2.1.5 Need, relevance and priority of the study

Irritability (including anger and aggression) occurs commonly in HD patients, but current treatments for these behaviors are empirical or based on small, unblinded clinical trials. Repurposed antidepressant, anxiolytic, and antipsychotic drugs are the mainstays of therapy. We feel that evaluating the scales that are available for assessing irritability, as well as anger and aggression in HD patients, is an especially compelling feature of the work proposed. Actual comparative data about how these scales perform in a clinical trial will be obtained in our target population. This will help us design and power a future efficacy study. Examining the safety and tolerability of our drug at the same time that we collect information about the scales that might be used in Phase IIb and Phase III trials is efficient in terms of both time and overall cost.

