6.13.6.5 HD Clinical Assessments using the UHDRS '99 Rating Scale

Since 1993 the HSG has developed, tested, and refined a comprehensive clinical research instrument, the Unified Huntington's Disease Rating Scale '99 (UHDRS). The instrument assesses four major domains: motor function, cognitive function, behavioral abnormalities, and functional capacity. The scale was developed to be an efficient survey that is sensitive to different aspects of disease progression and to the disability or loss of function caused by HD. The HSG has established the inter-rater reliability and internal consistency of the scale (HSG 1996) and it has been used in all HSG clinical trials. Outcome variables derived from the UHDRS include the total motor score, total behavior frequency score, total behavior frequency x severity score, cognitive test scores (Symbol Digit Modalities Test, Verbal Fluency Test, Stroop Interference Test), Functional Checklist score, Independence Scale score, and Total Functional Capacity (TFC) score.

The disease-specific aspects of the UHDRS such as the total motor score are useful in understanding the variability in progression of HD and different disease phenotypes. The TFC is often considered the most clinically relevant component of the UHDRS because it focuses on key domains of function and uses simple scoring. It consists of five ordinal-scale items assessing a Subject's capacity in: occupation, financial affairs, domestic responsibilities, activities of daily living, and independent living. The sum of these items yields a TFC score that ranges from 0 (extreme incapacity) to 13 (full capacity). This score has been validated against radiographic measures of disease progression, including CT and MR measures of striatal volume and PET measures of striatal metabolism (Young 1986, Tabrizi 2012, Bamford 1989, Rosas 2008). The TFC shows a steady decline over the course of the illness and is especially sensitive to changes in the early and mid-stages of the disease (Marder 2000).

The UHDRS will be completed at designated visits as noted on the Schedule of Activities (APPENDIX A). The Motor and Behavioral subscales must be completed by the site Investigator. Qualified study staff may complete the Cognitive assessments if delegated by the site Investigator and designated on the Investigator, Study Staff and Related Duties Log. Clinical Status and Quality of Life Assessments.

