8.1.3 Exploratory Aim: Activity

The exploratory aim is to examine several measures of irritability and other problem behaviors, and clinical assessments for activity signal. The following measures will be compared to each other in order to examine relative effect sizes. The endpoint will be rate of change (slope) over 12 weeks.

Unified Huntington Disease Rating Scale (UHDRS)
Clinical Global Impression (Severity, CGI-S and Improvement, CGI-I)
Aberrant Behavior Checklist (ABC), irritability subscale

Cohen-Mansfield Aggression Inventory (CMAI)
Problem Behaviors Assessment – short form (PBA-s)
Irritability Scale (IS)
HD QoL
Caregiver Burden Questionnaire

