Suppose Y_{ij} is the irritability score for the i th patient ($i = 1, \dots, N$) at the j th week ($j = 1, \dots, n_i$), and t_{ij} denotes time in weeks. Assuming linear change over time, the LMM can be written as the following,

$$Y_{ij} = \alpha + \beta t_{ij} + \gamma t_{ij}g_{120i} + \delta t_{ij}g_{160i} + (a_i + b_i t_{ij} + \epsilon_{ij})$$

where g_{120i} is a dummy variable for the 120mg group membership (1 = in the group, 0 = otherwise), and g_{160i} is a dummy variable for the 160mg group. In the equation, α is the intercept (baseline level) that is common among groups due to random assignment; β is the slope for the placebo group; γ is the 120mg vs placebo slope difference; and δ is the 160mg vs placebo slope difference. The terms a_i and b_i are the random effects (random intercepts and slopes, respectively), and ϵ_{ij} is random error. We make the typical assumptions, $[a_i \ b_i]^T \sim \mathcal{N}(\mathbf{0}, G)$, $\epsilon_{ij} \sim \mathcal{N}(0, \sigma^2 I_i)$, and $[a_i \ b_i]^T \perp \epsilon_{ij}$.

An evaluation of the null hypothesis that the slopes are equal among the groups can be performed with the likelihood ratio test (LRT). The LRT is based on a comparison of the full model above and a reduced model omitting $\gamma t_{ij}g_{120i} + \delta t_{ij}g_{160i}$. Alternatively, a global effect size can be computed as the difference of Akaike's information criterion (AIC) for the full and reduced model (Burnham 2002). The statistical strategy is to estimate the full and reduced model for each irritability and clinical variable separately. Then the difference in AIC for each variable (full vs reduced model) can be used to assess relative strength of effect in discriminating among the groups. Because larger AIC differences indicate larger effect sizes (i.e., greater discrimination), the variable with the largest AIC difference (or the top few variables) will be a candidate for further study in clinical trials of efficacy. AIC differences of the irritability variables relative to the clinical variables will provide a context for judging the effect size of the former compared to general motor, cognitive, and functional variables in HD. The difference in AIC has been found to be a useful method of screening candidate variables for efficacy in HD research (Leoni 2013, Paulsen 2013).

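### Ranking irritability scales by AIC difference ignores direction and varies with missing data, and no usable effect estimates are promised: a cheap improvement

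*Protocol*

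**What the plan says.** Protocol Section 8.1.3 lists eight entries for the exploratory activity aim and says "The following measures will be compared to each other in order to examine relative effect sizes". Section 8.2 gives the method: "The statistical strategy is to estimate the full and reduced model for each irritability and clinical variable separately". The full model has a common intercept, a placebo slope and two slope differences (gamma for 120 mg, delta for 160 mg). The reduced model drops gamma and delta.

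A likelihood-ratio test of equal slopes is offered as something that can be done, with no significance level. As an alternative, "a global effect size can be computed as the difference of Akaike's information criterion (AIC) for the full and reduced model". Larger differences are read as larger effects, and then "the variable with the largest AIC difference (or the top few variables) will be a candidate for further study in clinical trials of efficacy". Clinical variables serve as context for judging the irritability scales.

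Section 8.2 states no minimum AIC difference, no condition on direction, no measure of rank uncertainty and no outcome in which nothing is selected. SAP Section 8.1 lists the scales, gives no model or ranking rule, and keeps these analyses out of the final study report. On the purpose of the comparison, Protocol Section 2.1.5 says "This will help us design and power a future efficacy study".

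**The concern.** A difference in AIC between nested models restates the likelihood-ratio statistic. That statistic measures evidence against equal slopes, so it mixes the size of the effect with the amount of data, and it has no sign. A scale on which the drug worsens irritability ranks as high as one on which the drug improves it. Of two equally sensitive scales, the one with fewer missing values ranks higher. Some scale always comes top, including when the drug is inert.

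At stake is the advice carried into the next trial: which scale to use, and what difference and SD to power on. The primary tolerability analysis and the Go/No-Go decision are not affected.

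**Working it through.** The plan states no operating figure for this ranking, so there is none to reproduce.

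**Inputs from the documents.** 36 per arm, three arms (Protocol Section 8). Two slope terms dropped (Section 8.2). Four irritability and behavior scales: ABC, CMAI, PBA-s and IS (Section 1.3), or five if the IS is counted once per rater, since Subject and Study Partner complete it separately (Section 6.13.6.3). Eight listed entries (Section 8.1.3).

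**Assumed, because the documents give no values.** Correlation between scales 0.3 to 0.7. Effects of 0.5 SD on the best scale and 0.3 SD on the others, where SD is that of the individual slope. 25% missing data on one scale, as an illustration.

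**1. What the metric is.** AIC(reduced) − AIC(full) = LRT − 2 × 2 = LRT − 4. With no drug effect, LRT follows chi-square on 2 df, so for one scale P(AIC difference > 0) = P(LRT > 4) = exp(−2) = 0.135. Fitting the Section 8.2 model by maximum likelihood to 600 null trials (weeks 0, 6 and 12, assumed variance components) gave a mean LRT of 2.03 (theory 2) and P(LRT > 4) = 0.133. The chi-square reference is therefore adequate at this sample size.

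**2. Direction and amount of data.** If both active arms differ from placebo by d SD, the noncentrality is (2n/3)d² for n per arm, and the expected AIC difference is about (2n/3)d² − 2. Because d is squared, +d and −d give the same value.
- n = 36, d = 0.5: 24 × 0.25 − 2 = 4.0.
- n = 27 (25% missing), d = 0.5: 18 × 0.25 − 2 = 2.5.

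**3. Use for powering.** Take an AIC difference of 4, so LRT = 8, and treat 8 as the noncentrality.
- Effect d in one or both active arms: 24d² = 8, so d = 0.58.
- Effects +d and −d in the two arms: 72d² = 8, so d = 0.33.

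Per-arm size for two-sided 5% and 80% power is 2(1.96 + 0.84)²/d², about 15.7/d². That gives 15.7/0.333 = 47.1, so 48 per arm, or 15.7/0.111 = 141.3, so 142 per arm. One AIC value fits both.

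**4. Behavior of the ranking.** Simulation with one slope per person, 36 per arm, 20,000 trials per setting, AIC difference = 108 ln(SST/SSW) − 4. Ranges run over the assumed correlations.

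| Quantity | 4–5 scales | 8 measures |
|---|---|---|
| No drug effect: at least one AIC difference > 0 | about 33–50% | about 46–65% |
| Best scale (0.5 v 0.3 SD) ranks first | about 50–70% | about 40–54% |
| Best scale is in the top three | about 86–97% | about 73–83% |

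A random ordering would put a given scale first in 1/4 = 25%, 1/5 = 20% or 1/8 = 12.5% of trials, and in the top three in 75%, 60% or 37.5%. The ranking carries information, but it does not identify a single best scale reliably.

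**The case against.** **It is a screen in an exploratory aim.** The text speaks of a candidate and allows the top few variables. Go/No-Go rests on tolerability, and the SAP leaves these analyses out of the final report. This stands. A reader might infer that the rule commits the sponsor to one winning scale; the wording does not support that, and the top-three figures show the screen doing better than the first-rank figures alone suggest.

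**The model already gives powering inputs.** Gamma, delta, the random-effect covariance and the residual variance are all estimated, and Section 8.2 says slope differences will be examined. So it would be wrong to say that the analysis yields nothing to power a trial with. What remains is that neither document commits to reporting these quantities with intervals, SDs or standardized values.

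**At equal N the ranking matches variance explained.** True. ABC, CMAI, PBA-s, IS, HD QoL and the caregiver questionnaire are scheduled at the same three visits, so visit dropout tends to affect them together. The dependence on missing data matters only if completeness differs between scales, which could happen because some need the Study Partner and some do not. The 25% is an illustration, not a forecast.

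**A null test is mentioned.** It is, but it is optional, has no stated level and does not govern which scales go forward.

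**The number of candidates.** Section 6.13.6.5 says "Outcome variables derived from the UHDRS include the total motor score, total behavior frequency score, total behavior frequency x severity score" among others, and a reader might count some 16 or 17 competing variables and quote a much higher chance of a false lead. Section 8.2 gives clinical variables a context role, so 4 or 5 scales is the fairer headline count. CGI-S is taken only at Baseline and CGI-I only at Weeks 6 and 12, so neither fits the Week 0–12 slope model as listed.

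**Conclusion.** The point holds as a cheap improvement. The AIC difference is unsigned, depends on the number of participants with data, and always yields a top scale; the optional likelihood-ratio test does not change that. With an inert drug, about 33–50% of trials would show a positive value on at least one of the 4 or 5 irritability scales. A truly best scale would rank first in about 50–70%. With 8 measures the figures are about 46–65% and 40–54%.

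The algebra follows from the stated model. The percentages rest on assumed correlations and effect sizes and on a one-slope-per-person simplification. The null percentages also use a cut-off of zero that the protocol does not state; under the rule as written, a top scale is named every time.

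A reader might infer that a scale should go forward only after a multiplicity-adjusted likelihood-ratio test. The trial's size does not support that. A true 0.5 SD effect has noncentrality 24 × 0.25 = 6, and a Bonferroni test at 0.05/8 would pass it about 29% of the time, or about 21% at 0.05/17. Such a gate would discard most useful scales.

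**What to change.** Keep the AIC difference as a descriptive screen and add the following to the exploratory analysis text, in the SAP or a separate exploratory plan:

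- For each scale, report the signed slope difference for each dose against placebo (gamma and delta) with 95% confidence intervals, raw and standardized, using the same definition of SD for every scale.
- Report the SD or variance components and the percentage complete for each scale.
- Compare scales on the same participants, or on the standardized estimate.
- Bootstrap participants, resampling all scales together, and report how often each scale ranks first and in the top few.
- State that a scale is not called sensitive to drug effect if its AIC difference is not positive or its effect is in the wrong direction, and that finding no scale that stands out is an allowed conclusion.
- Do not add a multiplicity-adjusted likelihood-ratio gate.

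The condition of a positive AIC difference is a floor, not error control: the null figures above show how often noise passes it. The intervals and bootstrap ranks carry the uncertainty; they display the instability and do not remove it. The cost is some extra exploratory programming on data already collected, and a less definite recommendation.

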9 DATA AND SAFETY MONITORING, COLLECTION AND MANAGEMENT

9.1 Data Management

Data Management (DM) is the development, execution and supervision of plans, policies, programs, and practices that control, protect, deliver, and enhance the value of data and information assets.

All data will be managed in compliance with NeuroNEXT policies, and applicable Sponsor and regulatory requirements. The DCC is responsible establishing procedures to ensure that all aspects of clinical data management activities occur as required, and for properly instructing site personnel to collect, transcribe, correct, and transmit the data onto source documents, CRFs, and other forms used to report, track and record clinical research data.

Site personnel will collect, transcribe, correct, and transmit the data onto source documents, CRFs, and other forms used to report, track and record clinical research data. The DCC is responsible for developing, testing, and managing clinical data management activities. The DCC will monitor clinical sites to ensure compliance with data management requirements and Good Clinical Practices.

9.2 Registration

Registration of participants on this protocol will employ an interactive data system in which the clinical study site will attest to the participant's eligibility as per protocol criteria and obtain appropriate informed consent. NeuroNEXT CIRB approval for the protocol must be on file at the DCC before accrual can occur from the clinical study site.

The DCC will use a system of coded identifiers to protect participant confidentiality. When the participant is registered to participate in the study using the DCC-provided web-based registration, the system will assign a participant ID number. The unique ID code will include a protocol ID, a site ID, and a unique participant ID. To confirm the correct participant ID, the data entry system will require a second entry of the unique participant ID and compare for consistency. In this fashion, no personal identifiers would be accessible to the DCC and the data will be collected on the correctly identified Subject.

9.3 Data Entry

The general NINDS Common Data Elements (CDE) will be used to construct many of the data collection forms. All study data will be collected via systems created in collaboration with the DCC and will comply with all applicable guidelines regarding patient confidentiality and data integrity.

Data entry will occur at the enrolling clinical study sites. Data quality assurance and analyses will be performed by the DCC. The DCC, located at the University of Iowa, will coordinate all data and statistical services for the study, as well as on-site monitoring for all participating clinical study sites.

Data collection for this study will be accomplished with online electronic case report forms. Using encrypted communication links, online forms will be developed that contain the requisite data fields.

9.4 Quality Assurance

By signing this protocol, the Sponsor and Investigator agree to be responsible for implementing and maintaining quality control and quality assurance systems with written standard operating procedures (SOPs) to ensure that studies are conducted and data are generated, documented, and reported in compliance with the protocol, accepted standards of GCP, and all applicable federal, state, and local laws, rules and regulations relating to the conduct of the clinical study.

9.5 Development of Monitoring Plan

Onsite monitoring visits will be conducted by DCC monitors according to a pre-defined Monitoring Plan. The monitoring plan will detail the frequency of on-site visits, the study data to be monitored, the review of any regulatory files, drug and supplies accountability (if applicable), documentation of the on-site visit, and the resolution process for data errors that are discovered during the visits. All participating clinical study sites will be monitored at least once after a study initiation visit and all sites will have a close-out visit for each protocol. One on-site monitoring visit is anticipated for each clinical study site per year. All Subjects will be monitored for inclusion and exclusion criteria, informed consent procedures, and adverse events. A certain percentage of data is also monitored/ source data verified against the data entered into the study database. The monitoring plan will include flexibility to revise the frequency of visits or data monitored depending on clinical study site or study related issues.

9.6 Site Monitoring Visits

All aspects of the study will be monitored by qualified individuals. Monitoring will be conducted according to Good Clinical Practice (GCP) and applicable government regulations. The Investigator agrees to allow monitors access to the clinical supplies, dispensing and storage areas, and to the clinical files of the study Subjects, and, if requested, agrees to assist the monitors.

On-site monitoring visits will be conducted by DCC monitors according to a pre-defined monitoring plan for each protocol. The goal of on-site monitoring is to analyze (review) the data as it is collected, to check the validity and integrity of the data, to verify source documentation, to ensure protection of human Subjects, and to ensure protocol compliance with federal regulations. During the monitoring visit, the monitor assesses the overall status of the study, staff, and facilities to determine whether the study is being conducted per protocol and in compliance with regulatory requirements. The monitor also conducts a CRF review that includes checks of all adverse event documentation, verifies the presence of all critical correspondence and records related to investigational products and clinical supplies (if applicable), and determines if protocol violations have occurred and are documented properly.

After the monitoring visit, the monitor documents the results of the monitoring visit and completes a post-visit monitoring letter that conveys any issues discovered during the visit and the need for data corrections, if appropriate. Drug and supplies accountability may also be monitored during the site visit. The DCC will work closely with the CCC to monitor and document drug distribution from the manufacturers to the clinical study sites (CSS). Each CSS will be provided with a drug accountability log which will be reviewed by the DCC monitors and reconciled with distribution logs. At study closeout the DCC and CCC will confirm that appropriate data have been reviewed, source documentation has been verified, and all required documents are present in the Study Regulatory File.

9.7 Laboratory Data Flow

The DCC will provide laboratories with online forms and/or electronic data exchange mechanisms - depending on their capabilities and needs - to enter, update and obtain relevant data. When a blood or urine sample has been obtained, the clinical study site study Coordinator will send the sample (participant ID, site ID, and protocol ID numbers will be used) to the University of Rochester central laboratory. Results will be sent via a secure system to University of Rochester laboratory with no individual-identifying information on the report. The laboratory will electronically communicate the test results to the respective clinical study sites in a secure manner. The laboratory will also transfer test results electronically to the DCC.

9.8 Safety Monitoring

Safety monitoring will include careful assessment and appropriate reporting of adverse events (AEs). Medical monitoring will include contemporaneous assessment of serious adverse events. Refer to Section 10 for AE definitions and additional information.

The monitoring of Subject safety and data quality will follow the NINDS Guidelines for Data and Safety Monitoring in Clinical Trials. A Data and Safety Monitoring Board (DSMB) appointed by the NIH/NINDS will meet at six-month intervals (or as determined by the NINDS) to review partially unblinded study data provided by the study statistician. This committee will monitor rates of adverse events and endpoints in the trial and will monitor the performance of the trial. The frequency and format of DSMB meetings, reports, and guidelines will be agreed upon prior to study Subject enrollment.

An Independent Medical Monitor (IMM) will be appointed to review all adverse events, in a blinded fashion, on a periodic basis. In addition, the IMM will review all events that meet the regulatory definition of a Serious Adverse Event, upon receipt of notification via the Electronic Data Capture (EDC) system.

FDA, Office of Human Research Protection (OHRP), and NeuroNEXT CIRB requirements for reporting AEs will be followed. Subjects will be monitored for AEs from the time they are randomized until 30 days following permanent discontinuation of study drug. At that point, all ongoing AEs will be followed to resolution or stabilization, whichever occurs first, but no new AEs will be recorded. The IMM/DSMB will review cumulative AEs; the frequency of this review will be determined by the IMM/DSMB.

For the purposes of this study, before randomization, only those adverse events, serious and non-serious, that in the opinion of the Investigator are deemed related to study procedures will be reported. After randomization, all adverse events will be reported.

Each Clinical Study Site Principal Investigator and research team (co-investigators, research nurse, clinical trial coordinator) are responsible for identifying and reporting AEs and determining the relationship of the event to the study drug/study procedures. Aggregate reports blinded by treatment group, detailed by severity, attribution (expected or unexpected), and relationship to the study drug/study procedures, will be prepared by the DCC. A separate report detailing protocol compliance will also be available monthly from the DCC. A determination will be made as to whether the protocol or informed consent document requires revision based on these reports.

The adverse event (AE) definitions and reporting procedures provided in this protocol comply with all applicable United States Food and Drug Administration (FDA) regulations and International Conference on Harmonization (ICH) guidelines. The site Investigator will carefully monitor each Subject throughout the study for possible adverse events. All AEs will be documented on CRFs designed specifically for this purpose. It is important to report all AEs, especially those that result in permanent discontinuation of the investigational product being studied, whether serious or non-serious.

Each clinical study site's Principal Investigator and research team are responsible for identifying adverse events and reporting them through the DCC Online Adverse Event Reporting System. Investigators are also responsible for complying with NeuroNEXT CIRB's reporting requirements for all safety reports. Copies of each report and documentation of IRB notification and receipt will be kept in the investigator's study file.

